**Eligibility criteria include the following:**

- Age 6 to less than 18 years at the enrollment visit
- Physician diagnosis of asthma, and
- History of an asthma exacerbation in the previous 12 months, defined as either:
  - Treatment with systemic corticosteroids,\* or
  - Increase in rescue medication use (i.e., abuterol or inhaled corticosteroid) for 24 hours or more, or
  - One or more missed school days due to asthma symptoms, or
  - An unscheduled visit for asthma at either a physician's office, urgent care, hospital emergency room, or
  - Hospitalization for asthma.

*\*In the event of a recent exacerbation treated with systemic corticosteroids or requiring hospitalization, the first study visit will be postponed until two weeks after the last dose of systemic corticosteroids (i.e., prednisone or prednisolone).*

These criteria should ensure a study population with sufficient disease burden, since several prior studies in children have identified these risk factors as significant predictors of poor asthma control and poor future outcomes. Indeed, several prior studies in children have identified a recent exacerbation as the strongest risk factor for subsequent exacerbations regardless of disease severity or use of controller medications. In the third iteration of the NHLBI Severe Asthma Research Program (**SARP**, [name] co-investigator), exacerbations occurred in 39.7% of enrolled children by one year (unpublished data), similar to reports in other cohorts. In SARP, an exacerbation in the previous year was also associated with an 8.94-fold increase in the odds of future exacerbation by one year (95% CI: 4.37, 18.69). Poor asthma symptom control at baseline was similarly associated with increased odds of future exacerbation (OR 2.65, 95% CI: 1.44, 4.82), but there was no additive effect with prior exacerbation. Therefore, we have elected to enroll participants irrespective of asthma symptom control. This will not only facilitate enrollment of participants, but will also promote symptom heterogeneity (which is essential for symptom clustering) and the likelihood of biomarker detection (since inflammation will also be heterogeneous).

**Exclusion criteria for Option 1, a single study visit with telephone/email and electronic medical record follow-up for up to 48 weeks, include:**

- Pregnancy,
- Current smoking,
- Congenital disorders or deformities of the chest wall, lungs or airways,

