#### **H. Rationale for triamcinolone acetonide injection**

At the completion of the baseline visit, a subset participants who consented to the 48 week cohort study will receive intramuscular triamcinolone acetonide (Kenalog,® 1 mg/kg, up to 40 mg maximum) administered deep in the gluteal muscle by a trained registered nurse. Corticosteroids are the cornerstone of treatment for asthma; intramuscular triamcinolone was selected as the treatment of choice over oral prednisolone or inhaled corticosteroids to allow for characterization of corticosteroid insensitivity without the confounding effects of poor adherence or inadequate drug delivery or absorption. We further considered the pharmacology of corticosteroids. Because triamcinolone has 20% more glucocorticoid activity than prednisolone, triamcinolone 1 mg/kg will ensure that participating children have a sufficient dose of corticosteroid to achieve the desired potential anti-inflammatory effects. In previous studies of adults, a single dose of 80 mg of triamcinolone significantly improved lung function and asthma symptoms in the majority of patients. Given several previous studies in children and our own published studies of triamcinolone responsiveness in children with asthma, a dose of 1 mg/kg of triamcinolone should elicit a clinical response. Because inclusion is limited to children with a recent exacerbation (many of whom will have poor symptom control and all of whom are at risk for future exacerbation), all participants have the potential to benefit from this procedure. The safety of our dosing strategy has also been well established. In our previous study ([name] R01NR012021), the triamcinolone injection was well tolerated and no unexpected adverse events were reported. Expected adverse events

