**Table 2. Blood collection procedures**

**Urine collection for pregnancy testing.** Urine will be collected in females of child-bearing potential by clean-catch methods for the purpose of pregnancy testing. Unused urine will be discarded.

**Sputum induction.** Sputum induction will be performed in participants 12 years and older after pre-treatment with 4 inhalations of albuterol sulfate delivered through a MDI and holding chamber. 3% saline (substitutions permitted) will be inhaled through an ultrasonic nebulizer for a maximum of 12 minutes, with breaks every 2 minutes. To ensure safety, the procedure will only be performed on children with a post-bronchodilator FEV1 of >70% predicted; spontaneous sputum samples may be collected on children with an FEV1 below

these limits. A physician will be available during the challenge; study staff will calculate and record the FEV1 value that equals both a 10% and 20% fall in lung function based upon the recorded post-bronchodilator FEV1 values. Participants will not be discharged until their FEV1 is within 10% of their post bronchodilator FEV1 and will be given albuterol sulfate (2 inhalations as needed) for this purpose. Sputum samples will be processed by the [name] laboratory.

**Triamcinolone acetonide injection.** Each participant who meets inclusion/exclusion criteria will receive triamcinolone acetonide intramuscularly at the end of visit 1. Children 6-21 years will receive 1 mg/kg triamcinolone acetonide (up to 40 mg maximum).

Triamcinolone acetonide will be administered as a single intramuscular dose deep in the gluteal region.

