**Triamcinolone injection.** Triamcinolone acetonide injectable suspension (Kenalog®, 40 mg/mL) provides a synthetic corticosteroid with anti-inflammatory action. Triamcinolone acetonide is FDA-approved and indicated for children 6 years of age and older with asthma. The suggested initial dose for children 6-12 years of age is 40 mg, although dosage depends more on the severity of symptoms than on age or weight. For this protocol, children will receive 1 mg/kg in one intramuscular dose (up to 40 mg maximum). Although local side effects of intramuscular administration have been reported, including pigmentation changes and subcutaneous and cutaneous atrophy, these side effects are minimized by deep injection into the gluteal muscle. All triamcinolone acetonide injections will be administered by an experienced pediatric registered nurse. Systemic side effects with a single triamcinolone acetonide injection (40 mg max) are rare and triamcinolone acetonide injection is thought to be generally safe in children. Recent studies of much higher doses of intramuscular triamcinolone acetonide in children with nephrotic syndrome (~2 mg/kg) and difficult-to-treat asthma (60 mg) have revealed little side effects and good tolerance of the medication, with no reported incidence of cataracts, diabetes, added weight gain, or arterial hypertension. Although repeated use of triamcinolone was associated with slightly decreased growth velocity during the active treatment phase (2 mg/kg injection each month for up to 36 months), growth velocity returned to normal after discontinuation of triamcinolone therapy. Nonetheless, participating children will be screened thoroughly by the study physician for the presence of any co-morbid conditions that may increase the risk of triamcinolone acetonide administration. Children receiving triamcinolone acetonide will be educated about signs of potential complications and will have

24-hour access to an on-call pediatric physician. Participants will also undergo a comprehensive evaluation 2 weeks after the triamcinolone acetonide is administered.

Triamcinolone acetonide is a pregnancy category C medication and will not be administered to pregnant adolescents due to potential virilizing effects on the fetus.

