Because LTA is aimed at characterizing transition over time, it requires variability in all variables. Therefore, we will perform LTA with patient-reported symptoms (global, mental, social and physical health categories) and measures of asthma disease activity (ACQ, ACT, lung function, exhaled nitric oxide, blood eosinophils) measured at baseline and visits 3, 4 and 5 (**see Appendix 1**). Age, sex, race, ethnicity, socioeconomic status, medications, exposures and allergic sensitization measured at the baseline visit will be considered stable and treated as covariates in the LTA model. All participants will be included in the analysis since missing data for the variables are handled in the procedure, with data assumed to be missing completely at random. The test of the null hypothesis that data are missing completely at random (Missing Completely At Random test in the SAS LTA procedure) will be evaluated; if non-significant, missingness does not affect the interpretation of the results. The number of classes will be statistically determined using the Bayesian information criterion (**BIC**) and class prevalence if BICs are of a similar magnitude, to avoid a solution leading to low prevalent groups (<5%). To assess the stability of the group structure, goodness of fit of the “constrained” LTA model in which identical item-response probabilities across time are estimated (i.e., the same cluster structure is forced into multiple time points) will be compared with the “unconstrained” LTA model in which item response probabilities are estimated at each time point. To further address sex as a biological variable, models will also be fitted by sex, with statistical comparison of results observed in boys and girls. All analyses will be performed with SAS software version 9.4 (SAS Institute) using the PROC LTA procedure.

The primary outcome will be assessed after assignment of individuals to the latent classes that they had the highest probability of belonging to (based on the posterior probability provided by the model at baseline). A straightforward analysis of the primary outcome will follow and involves comparison of the proportion of children achieving a minimally importance difference in ACQ of at least 0.5 in each of the latent classes via a Chi-Square test.

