The secondary outcome, quality of life, will be compared with generalized estimating equations at visits 3, 4 and 5 using latent class assignment as the predictor. Analyses will be evaluated in light of pertinent covariates such as age, sex, race, ethnicity, socioeconomic status, medications, exposures and allergic sensitization. A 0.05 significance threshold will be utilized for secondary analyses without adjustment for multiple comparisons.

Metabolomic data, cytokine data, and amino acid data will be quantitative, linear mixed effects models will be used to determine the association between these symptom cluster group assignment.

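### Triamcinolone exposure varies with body weight under the capped dose, but the primary class comparison is an unadjusted chi-square with no weight- or age-adjusted analysis beside it

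*Combined protocol and SAP*

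**What the plan says.** Section L fixes the dose: "Children 6-21 years will receive 1 mg/kg triamcinolone acetonide (up to 40 mg maximum"). Sections H, N and R give the same rule with the same cap. Section H explains why an injection was preferred to oral or inhaled treatment, namely to characterise insensitivity "without the confounding effects of poor adherence or inadequate drug delivery or absorption". It then argues sufficiency per kilogram: "a dose of 1 mg/kg of triamcinolone should elicit a clinical response". Section R (triamcinolone injection) gives 40 mg as the suggested starting dose at ages 6 to 12 and adds "although dosage depends more on the severity of symptoms than on age or weight".

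In Section U (aims 1-3), each child is assigned to the most probable class at baseline. Then "A straightforward analysis of the primary outcome will follow": the classes are compared on the proportion reaching a "minimally importance difference in ACQ of at least 0.5 in each of the latent classes via a Chi-Square test". No covariate, stratum or sensitivity analysis is attached to this test. Age, sex, race and other baseline items are covariates in the latent transition model. The next paragraph, on quality of life, adds: "Analyses will be evaluated in light of pertinent covariates such as age, sex, race, ethnicity, socioeconomic status, medications, exposures and allergic sensitization". Neither list contains weight or dose received. Section K lists weight among the visit 1 measurements.

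The age range is stated in two ways. The eligibility list in Section E has "Age 6 to less than 18 years at the enrollment visit", whereas the opening of Section E, Sections I and L, and Appendix I run up to 21.

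**The concern.** Aim 2 predicts that the class with the worst symptoms will respond least to corticosteroids, and the primary test is how that prediction is examined. The injection removes adherence and absorption as explanations for a poor response. It does not give everyone the same exposure: with a per-kilogram dose and a fixed ceiling, exposure depends on weight on either scale that one might use. Both stated age ranges plausibly put participants on each side of 40 kg.

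If one class is heavier or older than another, a gap in responder rates has at least two readings: the class is less sensitive to the drug, or its members had a different exposure or body size. The planned test cannot tell these apart, and nothing beside it would show whether the second reading is a live one.

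**Working it through.** **The plan's own figure.** Section T gives power 0.808 for N = 147, 3 degrees of freedom, W = 0.275, alpha 0.05. With noncentrality N × W² = 147 × 0.0756 = 11.12, the noncentral chi-square gives 0.8084. All 45 cells of Table 3 reproduce to within 0.0014. The sample size arithmetic is not in dispute.

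**Exposure by weight.** Dose in mg = min(weight, 40); mg/kg = min(weight, 40) / weight. This follows directly from the stated rule.

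| Weight (kg) | Dose (mg) | mg/kg |
|---|---|---|
| 20 | 20 | 1.00 |
| 30 | 30 | 1.00 |
| 40 | 40 | 1.00 |
| 50 | 40 | 0.80 |
| 60 | 40 | 0.67 |
| 70 | 40 | 0.57 |
| 80 | 40 | 0.50 |

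Per kilogram, the heavier children receive less. In absolute milligrams, the lighter children receive less.

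**Size of a spurious difference between two classes (assumed inputs).** Difference = (share above 40 kg in class A − share in class B) × (gap in response between children at or below 40 kg and those above it). Assume a gap of 10 to 20 points.
- Shares 80% and 20%: 0.60 × 0.10 to 0.20 = 6 to 12 points.
- Shares 70% and 40%: 0.30 × 0.10 to 0.20 = 3 to 6 points.

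**Effect on the primary test (assumed inputs).** Take N = 147 in four equal classes with no true class effect. Response is 60% at or below 40 kg and a lower value p above it, so a class with share s above 40 kg has rate 0.60(1 − s) + p·s. Then W² = mean squared deviation of the class rates / [mean rate × (1 − mean rate)], and the rejection rate comes from the noncentral chi-square with 3 degrees of freedom and noncentrality 147 × W².

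One case in full: shares 20/40/60/80% and p = 40% give class rates 56, 52, 48 and 44%, with mean 50%. The mean squared deviation is (0.0036 + 0.0004 + 0.0004 + 0.0036)/4 = 0.0020. So W² = 0.0020/0.25 = 0.008, the noncentrality is 1.18, and the test rejects in 12.8% of trials.

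| Shares above 40 kg in the four classes | p = 50% | p = 40% | p = 30% |
|---|---|---|---|
| 50/50/50/50 | 5.0% | 5.0% | 5.0% |
| 35/45/55/65 | 5.4% | 6.8% | 9.2% |
| 20/40/60/80 | 6.8% | 12.8% | 24.7% |
| 10/10/90/90 | 11.2% | 33.9% | 68.7% |

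These share patterns are symmetric about one half, so the same rates hold if it is the lighter children who respond less. In simulation (4,000 runs for each of the nine unequal-share cells), a Cochran-Mantel-Haenszel test stratified at 40 kg rejected in 4.8 to 5.8% of trials. That good behaviour is partly built in, because response was assumed to change only at 40 kg. In practice mg/kg keeps falling above the cap, so some imbalance could remain within the upper stratum.

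**The case against.** The other side has several good arguments.

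- **Section H is about route.** It compares an injection with oral and inhaled treatment on adherence, delivery and absorption, and it states the cap at the outset. A reader might infer that the protocol promised equal exposure per kilogram and broke that promise. The text does not say so.
- **The relevant dose scale is not settled.** Section R plays down weight, and Section H cites a flat 80 mg dose in adults. A reader might infer that children above 40 kg are the under-exposed ones. The documents do not establish this, since in absolute milligrams the order reverses. The objection changes the direction of the concern but does not remove it: exposure depends on weight either way.
- **Age in the class model proves nothing about weight.** A covariate permits an association with class; it does not create one. The class indicators are symptom scores, asthma control, lung function, exhaled nitric oxide and eosinophils. That classes will differ in weight is an inference the documents do not support. They may.
- **Unadjusted proportions are a legitimate target.** Section B speaks of clusters predicting responsiveness and of associations with outcomes, and Table 3 powers a chi-square test. This stands, and it is why the chi-square should stay.
- **Adjustment has limits.** Above 40 kg, mg/kg is exactly 40/weight, so no model here can separate dose from body size, and adjusting could absorb part of a genuine class difference. This also stands.

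It might be added that age is already considered. In the class model it acts on membership. The later covariate sentence belongs to the quality-of-life paragraph; even if it reached the primary outcome, its open-ended list does not name weight or dose, and a plain chi-square cannot carry covariates.

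**Conclusion.** The point holds in a conditional form. It is certain that exposure varies with weight under the stated rule, that the primary test is unadjusted, and that weight and dose appear in neither covariate list. It is not known whether the classes will differ in weight or age, or whether response depends on exposure or body size within this range. With equal weight distributions across classes there is no bias.

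The 3 to 12 points, and the rejection rates between 5.4% and 68.7% under unequal shares, rest wholly on assumed shares and response gaps. They illustrate and do not estimate. For scale, the planned W = 0.275 equals a 27.5-point gap if two classes are high, two are low and the mean response is 50% (assumption). Large inflation of the false-positive rate needs strong separation by weight or a response gap of 20 to 30 points. A reader might conclude that the primary test is invalid and must be replaced; the documents do not support that. What is missing is a safeguard on interpreting a class difference as corticosteroid insensitivity.

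**What to change.** Leave the dosing unchanged and keep the chi-square as the primary test, so that Table 3 still applies. Add to Section U (aims 1-3):

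1. A prespecified supporting analysis of the primary outcome: logistic regression of response on class, adjusted for visit 1 weight (or mg/kg derived from it) and age. A Cochran-Mantel-Haenszel test stratified at 40 kg is a simpler alternative. Weight is the more neutral covariate, because mg/kg is constant up to 40 kg and absolute mg is constant above it.
2. A table of weight and mg/kg by class, and of responder rates by class at or below and above 40 kg.
3. A rule that any conclusion of class-specific corticosteroid insensitivity depends on consistency with the adjusted result.

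Separately, the protocol should reconcile Section H, which argues sufficiency per kilogram, with Section R, which gives weight a lesser role. It should also reconcile the two upper age limits (under 18 in the eligibility list, up to 21 elsewhere), since they affect how many participants exceed 40 kg.

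The cost is SAP wording and one table. Weight is already measured; the administered dose is not listed as a recorded item, but the intended dose follows from weight and the rule. The downsides are slightly less precision, because weight and age are correlated, and the fact that adjustment cannot separate dose from body size.

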#### **M. Non-study drugs**

Because this study is not a treatment trial, any medication considered necessary for the medical management and welfare of the participant may be given at any time. Participation in this study will also not prohibit access to new or novel therapies. Medications will not be withheld.

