### **Option 2: A 48-week cohort study with scheduled study visits**

Visit 1 (enrollment) will involve informed consent and participant characterization for the purpose of symptom cluster identification and receipt of systemic triamcinolone acetonide. Visit 2 will involve assessment of triamcinolone responsiveness. Visits 3, 4 and 5 are follow-up visits to assess the temporal stability of the symptom clusters. Visits 3, 4 and 5 can be completed in person or over the telephone.

This research is considered a clinical trial, because it involves an intervention (triamcinolone injection), and the study is designed to evaluate the efficacy of the intervention on symptoms and quality of life. The Emory Office of Clinical Research will facilitate the registration, periodic updates, and results reporting within ClinicalTrials.gov for the duration of the study.

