## J. Outcome measures

Asthma exacerbations are an outcome of interest for all participants.

For participants enrolled in the 48-week cohort study, the primary outcome is corticosteroid treatment responsiveness, assessed 14 days after systemic triamcinolone administration (at visit 2). Responsiveness will be determined from the mean difference in the Asthma Control Questionnaire (**ACQ**) score between visit 1 (baseline) and visit 2 (14 days), with a reduction of 0.5 considered a minimally important difference.

The secondary outcome for participants enrolled in the 48-week cohort study is quality of life, assessed by the PROMIS Pediatric Asthma Impact Scale (**PAIS**) at visits 3, 4 and 5. As with all PROMIS measures, the PAIS is scored on the T-score metric, with higher scores reflecting more of the concept being measured. On the T-score metric, 50 is the mean of the reference population and 10 is the standard deviation; thus scores of 40 and 60 are one standard deviation lower and higher than the mean of the reference population, respectively.

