**Steroid Responsiveness visit (Visit 2), Study Week 2 (window +7 days)**

1. Brief physical examination (by RN) including height and weight performed
2. Medical history obtained
3. Urine pregnancy testing
4. Asthma control evaluation (Asthma Control Questionnaire and Asthma Control Test)
5. Administer PROMIS symptom questionnaires
6. Measure exhaled nitric oxide
7. Perform spirometry with oscillometry (with bronchodilator reversibility)
8. Perform venipuncture for:
  - a. Complete blood count with differential (Children's Healthcare of Atlanta)
  - b. Plasma and white blood cells for aim 3 ([name] laboratory)
9. Perform sputum induction with samples stored for aim 3 ([name] laboratory)

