**Final follow-up visit (Visit 5), Study Week 48 (window +4 weeks)**

1. Brief physical examination (by RN) including height and weight performed\*
2. Medical history obtained
3. Urine pregnancy testing\*
4. Asthma control evaluation (Asthma Control Questionnaire and Asthma Control Test)
5. Administer PROMIS symptom questionnaires

6. Measure exhaled nitric oxide\*
7. Perform spirometry with oscillometry (with bronchodilator reversibility)\*
8. Perform venipuncture:
  - a. Complete blood count with differential (Children's Healthcare of Atlanta)
  - b. Plasma and white blood cells for aim 3 ([name] laboratory)
9. Perform sputum induction with samples stored for aim 3 ([name] laboratory)\*

\*procedure will not be performed in follow-up occurs by telephone

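### The primary responder rule ignores non-study systemic corticosteroids given between the triamcinolone injection and visit 2, so some improvements cannot be attributed to the injection

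*Combined protocol and SAP*

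**What the plan says.** Section I (Option 2) gives the purpose of the second visit: "Visit 2 will involve assessment of triamcinolone responsiveness". Section J makes corticosteroid responsiveness at 14 days the primary outcome and derives it from the ACQ difference between visits 1 and 2, with 0.5 as the minimally important difference. Section K lets visit 2 fall up to 7 days late, so the interval is 14 to 21 days.

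Section U tests this outcome with a chi-square comparison of the "proportion of children achieving a minimally importance difference in ACQ of at least 0.5 in each of the latent classes". It sets no condition on treatment received in between. Medications appear elsewhere in Section U, as baseline covariates of the latent transition model and as covariates for the secondary outcome. Neither use affects the primary test.

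Section M states that "any medication considered necessary for the medical management and welfare of the participant may be given at any time", and Section O sets no failure criteria. The only interval tied to systemic corticosteroids is an eligibility footnote in Section E, under which "the first study visit will be postponed until two weeks after the last dose of systemic corticosteroids". The visit 2 and visit 5 procedures in Section K have no corresponding rule. At visit 5 the blood draw includes a complete blood count and "Plasma and white blood cells for aim 3".

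**The concern.** Section H chose an injected drug over oral or inhaled corticosteroid so that insensitivity could be characterised without confounding by adherence, delivery or absorption. A second systemic course between injection and visit 2 is another confounder of the same measurement, and the responder rule cannot see it. A child injected at visit 1, treated with oral corticosteroid a few days later and improved by 0.5 at visit 2 is scored the same as a child who improved on the injection alone.

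Aim 2 expects the class with the poorest symptoms to respond least. Crediting extra courses as response raises observed responder rates. If the courses fall mostly in that class, its rate moves toward the others and the contrast under test shrinks. If they fall evenly on non-responders in all classes, the contrast still shrinks, but less.

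A smaller version arises at visit 5, where a blood count or Aim 3 sample may be taken shortly after a systemic course with nothing in the analysis to mark it.

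**Working it through.** **1. The plan's own power figure.** Inputs from Section T: N = 147, 4 clusters (df = 3), W = 0.275, two-tailed alpha 0.05. Noncentrality = N × W² = 147 × 0.275² = 11.12; critical chi-square = 7.81; power = 0.808, as in Table 3. Enrolment also agrees: 147 / 0.85 = 173. The power calculation is sound. The issue is the endpoint definition.

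**2. How many children could be affected.** The documents give no rate of systemic corticosteroid use between visits 1 and 2. The nearest figures are yearly exacerbation proportions: 39.7% (Section E, a severe-asthma research cohort) and 53.7% (Section A, children with asthma nationally). Assuming a constant rate:

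- Rate = −ln(1 − p): 0.506 per year for 39.7%; 0.770 per year for 53.7%.
- P(event in d days) = 1 − exp(−rate × d/365).

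| Yearly figure | 14 days | 21 days | Of 147 children | Of a class of 37 |
|---|---|---|---|---|
| 39.7% | 1.9% | 2.9% | 2.8 to 4.2 | 0.7 to 1.1 |
| 53.7% | 2.9% | 4.3% | 4.3 to 6.4 | 1.1 to 1.6 |

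The class of 37 is 147 / 4. These counts are exacerbations of any kind. A misclassified child must also have received systemic corticosteroids, must still show an ACQ fall of at least 0.5 at visit 2, and must not have reached that fall on the injection alone. Misclassifications are therefore fewer than these counts. The base of 147 is itself too large if some participants choose Option 1, which has neither injection nor visit 2.

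**3. Effect on power (illustration).** Assume four equal classes with true response 0.60 in three and 0.283 in the poorest. The mean is 0.521, the between-class variance 0.01884, and W = √(0.01884 / (0.521 × 0.479)) = 0.275, matching the plan. Let a share r of true non-responders be counted as responders, so that p becomes p + (1 − p)r. Take r = 1.9% and 4.3%, the extremes of the table. This treats every exacerbation among non-responders as steroid-treated and followed by a 0.5 fall.

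| r | Where | Response, three classes | Response, poorest | W | Power |
|---|---|---|---|---|---|
| 0 | – | 0.600 | 0.283 | 0.275 | 0.808 |
| 1.9% | all classes | 0.608 | 0.297 | 0.270 | 0.79 |
| 4.3% | all classes | 0.617 | 0.314 | 0.264 | 0.77 |
| 1.9% | poorest only | 0.600 | 0.297 | 0.263 | 0.77 |
| 4.3% | poorest only | 0.600 | 0.314 | 0.248 | 0.71 |

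The poorest class's responder rate is overstated by 0.297 − 0.283 = 1.4 points to 0.314 − 0.283 = 3.1 points.

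**4. Visit 5.** By the 14-day figures in step 2, about 2-3% of visit 5 samples would fall within two weeks of an exacerbation, and fewer within two weeks of a systemic course.

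**The case against.** The best defence is that the problem is small and the remedy is not neutral. The numbers affected are low, and a child who has just exacerbated may well miss the 0.5 threshold and be scored a non-responder anyway. An exacerbation soon after the injection does not prove insensitivity: Section F lists viral, allergen and other triggers. The outcome is named corticosteroid responsiveness, and prednisone is a corticosteroid. Counting every steroid-treated child as a non-responder mixes exacerbation, a separate outcome in Section J, into response. It would also lower the rate in any exacerbation-heavy class, in the direction that Aim 2 predicts.

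Most of this stands. It limits the size of the point and is why the composite rule needs sensitivity analyses beside it. It does not supply the missing rule. The outcome is tied to one injection, so improvement after a second course cannot be credited to it, whatever triggered the exacerbation.

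A reader might also infer that the Section E footnote shows the protocol already accepting that recent corticosteroids distort its measurements. The footnote gives no reason for delaying visit 1. It also covers hospitalisation, so letting the episode resolve is an equally natural reading. Nor could the same interval carry over to visit 2, which by design follows a systemic corticosteroid by two weeks.

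**Conclusion.** The gap is real and affects the primary endpoint for Option 2 participants: the written rule counts improvement after a non-study systemic course as response to triamcinolone. Its likely size is modest. At the documents' exacerbation rates, the ceiling is about 3 to 6 children in 147, or 1 to 2 in a class of 37. In the illustration, power falls from 0.808 to 0.77-0.79 (uniform) or 0.71-0.77 (poorest class only), before discounting for untreated exacerbations and for children who miss the threshold. Planned power is barely above 80%, so even the mildest of these cases takes it just below.

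The figures assume a constant exacerbation rate and borrow it from other populations. The injection may lower the rate; the requirement of a recent exacerbation may raise it.

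A reader might infer that clear drug failures are being scored as successes, with the poorest class overstated by 5 to 8 points (2 or 3 children of 37) or power falling to 0.24-0.31. The documents do not support this. Failure of the injection is not shown by an exacerbation alone, and 2 or 3 misclassified children exceed the 0.7 to 1.6 exacerbations of any kind expected in such a class. The lowest power figures need 20% of the poorest class's non-responders to be reclassified, for which there is no source. The visit 5 issue is secondary.

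**What to change.** In Sections J and U, before the outcome analysis that Section V places in Year 5:

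- Define response as an ACQ fall of at least 0.5 from visit 1 to visit 2 without non-study systemic corticosteroids between the injection and visit 2. Children who received them count as non-responders.
- Pre-specify two sensitivity analyses: one excluding these children, one using the ACQ-only rule. Report their number by latent class.
- Capture the dates of any systemic corticosteroid course in the medical history already taken at visit 2. The protocol does not say that dates are recorded, so the form may need a field.
- At visit 5, flag blood counts and Aim 3 samples taken within two weeks of a systemic course and repeat the models without them. No visit needs rescheduling.

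The cost is SAP wording, possibly one form field, and a few additional model runs. Clinical care under Section M is unchanged. The responder rate may be slightly lower, and the composite rule will include some exacerbations not due to steroid insensitivity; the sensitivity analyses will show how much that matters.
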